6.6.6.2 Dose Modifications Based on Haematologic Parameters

If a patient experiences a clinically significant and/or **unacceptable haematologic toxicity** (including a DLT) considered by the Investigator to be related to study intervention and not attributable to the disease (or to disease-related processes) under investigation, dosing in subsequent cycles will be withheld and may subsequently be restarted at one lower dose (equivalent to one dose reduction) and supportive therapy ([Appendix F](#)) administered as

required. Recommended dose modifications for haematologic toxicities associated with AZD0466 observed in patients with haematologic malignancies are shown in [Table 8](#).

Prior to the start of the next treatment cycle, patients must have a recovery of neutrophils $> 1000/\mu\text{L}$ and platelets $> 75\,000/\mu\text{L}$.

Table 8 Recommended Dose Modifications for Haematologic Toxicities

Toxicity grade	Occurrence	Action
Grade 3 or 4 neutropenia	Cycle 1	
 Continue AZD0466 Consider introducing growth factors (eg, G-CSF) after discussion with the Study Physician and continue to monitor ANC If Grade 4 > 7 days, discontinue AZD0466
	Cycle 2 and subsequent cycles	
 Withhold AZD0466 until ANC resolution to $\geq 1.0 \times 10^9/\text{L}$ Consider introducing growth factors (eg, G-CSF) and continue to monitor ANC If resolution occurs in ≤ 14 days, restart AZD0466 at same dose level, after discussion with Study Physician If resolution occurs in > 14 days but ≤ 21 days, restart AZD0466 at one lower dose (Table 7). A maximum of 3 dose reductions is permitted Discontinue AZD0466 if no resolution to ANC $\geq 1.0 \times 10^9/\text{L}$ in < 21 days
Febrile neutropenia/neutropenic infection (any grade lasting > 2 days)	Cycle 1	
 Consider introducing growth factors (eg, G-CSF), evaluate patient for infection, and begin antibiotic treatment per institutional guidelines Withhold AZD0466 until infection is resolved, and antibiotics are no longer required (except prophylactic antibiotics), and ANC $\geq 1.0 \times 10^9/\text{L}$ Restart at current dose after discussion with Study Physician
	Cycle 2 and subsequent cycles	
 Consider introducing growth factors (eg, G-CSF), evaluate patient for infection, and begin antibiotic treatment per institutional guidelines Withhold AZD0466 up to 21 days until infection is resolved, and antibiotics are no longer required (except prophylactic antibiotics), and ANC $\geq 1.0 \times 10^9/\text{L}$ 
 On first occurrence, restart AZD0466 at one lower dose (Table 7), after discussion with Study Physician On second occurrence, consider restart AZD0466 at one lower dose than the previous dose (Table 7), after discussion with Study Physician On third occurrence, restart AZD0466 at one lower dose than the previous dose (Table 7), after discussion with Study Physician unless there is no clear evidence of clinical benefit, then consider discontinuing AZD0466

Table 8 Recommended Dose Modifications for Haematologic Toxicities

Toxicity grade	Occurrence	Action
CTCAE Grade \geq 3 thrombocytopenia without the presence of significant bleeding	First occurrence	
 Withhold AZD0466 until values return to CTCAE Grade \leq 1 Restart AZD0466 at one lower dose (Table 7) if values resolve to CTCAE Grade \leq 1 within 14 days Discontinue AZD0466 if the above criteria are not met
	Second occurrence	
 Withhold AZD0466 until values return to CTCAE Grade \leq 1 Restart AZD0466 following the Q2W schedule (Table 6) if values resolve to CTCAE Grade \leq 1 within 14 days Discontinue AZD0466 if the above criteria are not met
	Third occurrence	
 Withhold AZD0466 until values return to CTCAE Grade \leq 1 Restart AZD0466 at one lower dose, maintaining the Q2W schedule (Table 6 and Table 7) if values resolve to CTCAE Grade \leq 1 within 14 days, there is clear evidence of clinical benefit and after discussion with Study Physician Discontinue AZD0466 if the above criteria are not met
	Fourth occurrence	
 Discontinue AZD0466
Presence of significant bleeding events with or without thrombocytopenia, such as: 
 Grade 3 or 4 haemorrhage Any intracranial haemorrhage or haematoma 	Any	
 Maintain platelets at $\geq 50 \times 10^9/L$ until resolution of bleeding Discontinue AZD0466

ANC = absolute neutrophil count; G-CSF = granulocyte colony-stimulating factor; Q2W = every 2 weeks.

6.6.6.3 Dose Modifications Based on Non-haematologic Parameters

Dose modifications for non-haematologic toxicities may occur at any time and the management are shown [Table 9](#). Special considerations for TLS and specific AEs are included in [Appendix F](#).

Dose modifications for changes in hepatic biochemistry are summarised in Section [6.6.6.4](#).

If a patient experiences a clinically significant and/or unacceptable non-haematologic toxicity (including a DLT), considered by the Investigator to be related to study intervention, and not attributable to the disease (or to disease-related processes) under investigation, dosing will be withheld or the dose reduced and supportive therapy administered as required.

Table 9 Dose Modifications for Non-haematologic Toxicities

Event	Occurrence	Action with AZD0466
Non-haematologic toxicities (except hepatic and cardiac changes, see Sections 6.6.6.4 and 6.6.6.5)		
CTCAE Grade 1 non-haematologic toxicities	Any	None
CTCAE Grade 2 non-haematologic toxicities	First occurrence	None
	Second occurrence	
 Withhold AZD0466 until resolution to CTCAE Grade ≤ 1 or baseline. Maximum dose hold 21 days Restart AZD0466 at same dose level Discontinue AZD0466 if no resolution to CTCAE Grade ≤ 1 or baseline in ≤ 21 days
	On third and subsequent occurrences	
 Withhold AZD0466 until resolution to CTCAE Grade ≤ 1 or baseline. Maximum dose hold 21 days Restart AZD0466 at one lower dose (Table 7). A maximum of 3 dose reductions is permitted Discontinue AZD0466 if no resolution to CTCAE Grade ≤ 1 or baseline in < 21 days
CTCAE Grade 3 non-haematologic toxicities	First occurrence	
 Withhold AZD0466 until resolution to CTCAE Grade ≤ 1 or baseline Supportive therapy should be given as per institutional guidelines If resolution occurs in ≤ 7 days, restart AZD0466 at the same dose level, after discussion with Study Physician If no resolution in ≤ 7 days, withhold AZD0466 for up to a total of 21 days If resolution occurs in > 7 days but ≤ 21 days, restart AZD0466 at one lower dose (Table 7) Discontinue AZD0466 if no resolution to CTCAE Grade ≤ 1 in < 21 days
	Second and subsequent occurrences	
 Withhold AZD0466 and provide supportive therapy as per institutional guidelines If resolution occurs in ≤ 7 days, restart AZD0466 at one lower dose (Table 7), after discussion with Study Physician If no resolution in ≤ 7 days, withhold AZD0466 for up to a total of 21 days If resolution to CTCAE Grade ≤ 1 in > 7 days but ≤ 21 days restart AZD0466 at one lower dose than the previous dose (Table 7) if there is clear evidence of clinical benefit and after discussion with Study Physician. A maximum of 3 dose reductions is permitted Discontinue AZD0466 if no resolution to CTCAE Grade ≤ 1 in ≤ 21 days.
CTCAE Grade 4 non-haematologic toxicities	Any	
 Discontinue AZD0466

CTCAE = Common Terminology Criteria for Adverse Events; Q2W = every 2 weeks.

6.6.6.4 Dose Modifications for Hepatotoxicity

AZD0466 dosing should be modified if a patient with normal or abnormal baseline liver function experiences a clinically significant and/or unacceptable change in hepatic biochemistry (including a DLT) described in [Table 10](#) and [Table 11](#) that is considered by the Investigator to be related to study intervention and not attributable to the disease (or to disease-related processes) under investigation.

Table 10 Dose Modification for Hepatotoxicity in Patients with Normal Baseline Liver Function

Event	Occurrence	Action with AZD0466
ALT and/or AST > 5 × ULN and ≤ 8 × ULN without concomitant elevation in bilirubin	First occurrence	
Withhold AZD0466 until values return to CTCAE Grade ≤ 1 or baselineRestart AZD0466 at same dose level if all values resolve to baseline or Grade ≤ 1 within 14 daysDiscontinue AZD0466 if the above criteria are not met
	Second occurrence	
Withhold AZD0466 until values return to CTCAE Grade ≤ 1 or baselineRestart AZD0466 at one lower dose (Table 7) if all values resolve to baseline or Grade ≤ 1 within 14 daysDiscontinue AZD0466 if the above criteria are not met
	Third occurrence	
Withhold AZD0466 until values return to CTCAE Grade ≤ 1 or baselineRestart AZD0466 following the Q2W schedule (Table 6) if all values resolve to baseline or Grade ≤ 1 within 14 days and after discussion with Study PhysicianDiscontinue AZD0466 if the above criteria are not met
	Fourth occurrence	
Withhold AZD0466 until values return to CTCAE Grade ≤ 1 or baselineRestart AZD0466 at one lower dose than the previous dose, maintaining the Q2W schedule (Table 6 and Table 7) if all values resolve to baseline or Grade ≤ 1 within 14 days, there is clear evidence of clinical benefit and after discussion with Study PhysicianDiscontinue AZD0466 if the above criteria are not met
ALT and/or AST > 8 × ULN and ≤ 20 × ULN without concomitant elevation in bilirubin	First occurrence	
Withhold AZD0466 until values return to CTCAE Grade ≤ 1 or baselineRestart AZD0466 at one lower dose (Table 7) if all values resolve to baseline or Grade ≤ 1 within 14 daysDiscontinue AZD0466 if the above criteria are not met
	Second occurrence	
Withhold AZD0466 until values return to CTCAE Grade ≤ 1 or baselineRestart AZD0466 following the Q2W schedule (Table 6) if all values resolve to baseline or Grade ≤ 1 within 14 days and after discussion with Study PhysicianDiscontinue AZD0466 if the above criteria are not met

Table 10 Dose Modification for Hepatotoxicity in Patients with Normal Baseline Liver Function

Event	Occurrence	Action with AZD0466
	Third occurrence	
 Withhold AZD0466 until values return to CTCAE Grade \leq 1 or baseline Restart AZD0466 at one lower dose than the previous dose, maintaining the Q2W schedule (Table 6 and Table 7) if all values resolve to baseline or Grade \leq 1 within 14 days, there is clear evidence of clinical benefit and after discussion with Study Physician Discontinue AZD0466 if the above criteria are not met
ALT and/or AST $\geq 3 \times$ ULN with concomitant elevation in bilirubin $\geq 2 \times$ ULN	Any occurrence	
 Discontinue AZD0466. Refer to Appendix E for process to follow in order to identify and appropriately report episodes of potential Hy's Law
ALT and/or AST $> 20 \times$ ULN	Any occurrence	
 Discontinue AZD0466

ALT = alanine aminotransferase; AST = aspartate aminotransferase; CTCAE = Common Terminology Criteria for Adverse Events; ULN = upper limit of normal; Q2W = every 2 weeks.

Table 11 Dose Modification for Hepatotoxicity in Patients with Abnormal Baseline Liver Function

Event	Occurrence	Action with AZD0466
ALT and/or AST $> 3.5 \times$ ULN and $\leq 5 \times$ ULN, without concomitant elevation in bilirubin	First occurrence	
 Withhold AZD0466 until values return to CTCAE Grade \leq 1 or baseline Restart AZD0466 at same dose level if all values resolve to baseline or CTCAE Grade \leq 1 within 14 days Discontinue AZD0466 if the above criteria are not met
	Second occurrence	
 Withhold AZD0466 until values return to CTCAE Grade \leq 1 or baseline Restart AZD0466 at one lower dose (Table 7) if all values resolve to baseline or Grade \leq 1 within 14 days Discontinue AZD0466 if the above criteria are not met
	Third occurrence	
 Withhold AZD0466 until values return to CTCAE Grade \leq 1 or baseline Restart AZD0466 following the Q2W schedule (Table 6) if all values resolve to baseline or Grade \leq 1 within 14 days, after discussion with Study Physician Discontinue AZD0466 if the above criteria are not met

Table 11 Dose Modification for Hepatotoxicity in Patients with Abnormal Baseline Liver Function

Event	Occurrence	Action with AZD0466
	Fourth occurrence	
 Withhold AZD0466 until values return to CTCAE Grade ≤ 1 or baseline Restart AZD0466 at one lower dose than the previous dose, maintaining the Q2W schedule (Table 6 and Table 7) if all values resolve to baseline or Grade ≤ 1 within 14 days, there is clear evidence of clinical benefit and, after discussion with Study Physician Discontinue AZD0466 if the above criteria are not met
ALT and/or AST $> 5 \times$ ULN and $\leq 8 \times$ ULN, without concomitant elevation in bilirubin	First occurrence	
 Withhold AZD0466 until values return to CTCAE Grade ≤ 1 or baseline Restart AZD0466 at one lower dose (Table 7) if all values resolve to baseline or Grade ≤ 1 within 14 days
	Second occurrence	
 Withhold AZD0466 until values return to CTCAE Grade ≤ 1 or baseline Restart AZD0466 restart following the Q2W schedule (Table 6) if all values resolve to baseline or Grade ≤ 1 within 14 days, after discussion with Study Physician Discontinue AZD0466 if the above criteria are not met
	Third occurrence	
 Withhold AZD0466 until values return to CTCAE Grade ≤ 1 or baseline Restart AZD0466 restart at one lower dose than the previous dose, maintaining the Q2W schedule (Table 6 and Table 7) if all values resolve to baseline or Grade ≤ 1 within 14 days and there is clear evidence of clinical benefit and after discussion with Study Physician Discontinue AZD0466 if the above criteria are not met
ALT and/or AST $> 8 \times$ and $\leq 20 \times$ ULN, without concomitant elevation in bilirubin	First occurrence	
 Withhold AZD0466 until values return to CTCAE Grade ≤ 1 or baseline Restart AZD0466 at one lower dose (Table 7) AND following the Q2W schedule (Table 6) if all values resolve to baseline or Grade ≤ 1 within 14 days, after discussion with Study Physician Discontinue AZD0466 if the above criteria are not met
	Second occurrence	
 Withhold AZD0466 until values return to CTCAE Grade ≤ 1 or baseline Restart AZD0466 at one lower dose than the previous dose, maintaining the Q2W schedule (Table 6 and Table 7) if all values resolve to baseline or Grade ≤ 1 within 14 days and there is clear evidence of clinical benefit and after discussion with Study Physician Discontinue AZD0466 if the above criteria are not met
	Third occurrence	
 Discontinue AZD0466

Table 11 Dose Modification for Hepatotoxicity in Patients with Abnormal Baseline Liver Function

Event	Occurrence	Action with AZD0466
ALT and/or AST $\geq 3 \times$ baseline with concomitant elevation in bilirubin $\geq 2 \times$ baseline	Any occurrence	
Discontinue AZD0466, refer to Appendix E for process to follow in order to identify and appropriately report episodes of potential Hy's Law
ALT and/or AST $> 20 \times$ ULN	Any occurrence	
Discontinue AZD0466

ALT = alanine aminotransferase; AST = aspartate aminotransferase; CTCAE = Common Terminology Criteria for Adverse Events; ULN = upper limit of normal; Q2W = every 2 weeks.

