Activated partial thromboplastin time (aPPT)		High-density lipoprotein (HDL)	Creatine kinase (CK)
Prothrombin time (PT)		Low-density lipoprotein (LDL)	
Fibrinogen		Pregnancy test (females of childbearing potential only)	
Viral Serology		Urine human chorionic gonadotropin (hCG)	Serum beta hCG
Hepatitis B and C	CMV	Others	
SARS-CoV-2		Serum immunoglobulins ^a	Beta-2 microglobulin ^a

^a At screening, at target dose (predose timepoint) and then as clinically indicated and at end of treatment visit.

^b Collected at screening, pre-infusion on each dosing day, and end of treatment visit.

Lipids: triglycerides, high density lipoprotein, low density lipoprotein, and cholesterol.

ACTH = adrenocorticotrophic hormone; ALT = alanine aminotransferase; AST = aspartate aminotransferase; BUN = blood urea nitrogen; CMV = cytomegalovirus; GGT = gamma-glutamyltransferase; LDH = lactate dehydrogenase; SARS-CoV-2 = severe acute respiratory syndrome coronavirus 2; TSH = thyroid-stimulating hormone; WBC = white blood cell.

NB. In case a patient shows an AST or ALT $\geq 3 \times$ ULN together with total bilirubin $\geq 2 \times$ ULN, refer to [Appendix E](#) for further instructions.

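### Table 11 (abnormal baseline liver tests): some patients with ALT or AST ≥ 3 × ULN and bilirubin ≥ 2 × ULN match no row, although the same ALT above 3.5 × ULN with normal bilirubin falls in a withhold row

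*Protocol*

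**What the plan says.** Appendix E 2 of the protocol defines potential Hy's Law in multiples of ULN only: ALT or AST ≥ 3 × ULN together with bilirubin ≥ 2 × ULN. The same limits appear in section 8.3.7, in the note under Table 12 that begins "NB. In case a patient shows an AST or ALT", and in SAP Table 4.

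Section 6.6.6.4 has two dosing tables. In both, action depends on the change being "considered by the Investigator to be related to study intervention and not attributable to the disease (or to disease-related processes) under investigation".

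- **Table 10 (normal baseline).** The combined row uses the Appendix E 2 limits, and the action is "Discontinue AZD0466. Refer to Appendix E for process to follow".
- **Table 11 (abnormal baseline).** The combined row also discontinues and also points to Appendix E, but its limits are ALT and/or AST ≥ 3 × "baseline with concomitant elevation in bilirubin" ≥ 2 × baseline. Three further rows (> 3.5 to 5, > 5 to 8 and > 8 to 20 × ULN) begin with "Withhold AZD0466 until values return to CTCAE Grade" 1 or baseline. Each applies only "without concomitant elevation in bilirubin", a phrase that is not defined. The last row discontinues above 20 × ULN.

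Section 6.6.6.3 says that for a related, unacceptable non-haematologic toxicity, including a DLT, dosing will be "withheld or the dose reduced and supportive therapy administered as required". The same section also says "Dose modifications for changes in hepatic biochemistry are summarised in Section" 6.6.6.4.

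**The concern.** Table 11 measures the combined rise against the patient's own baseline, measures the isolated transaminase rise against ULN, and makes the ULN rows conditional on no bilirubin rise. A patient can therefore meet the Appendix E 2 definition and fall between the two sets of rows. Using baseline-relative limits could explain why such a patient is not discontinued. It does not explain why a bilirubin rise should take the patient out of a withhold row that applies at the same ALT with normal bilirubin.

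What is at stake is patient safety. Table 1 lists hepatotoxicity as an important potential risk, section 8.3.6 makes it an AESI, and section 10.6.6.3 counts potential Hy's Law as a DLT in Cycle 1. For these patients the hepatic dosing table gives no instruction.

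**Working it through.** The plan has no figure to reproduce. The check is whether the rows of Table 11 cover every case.

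**Inputs.** On-study ALT is A, baseline ALT is A0, on-study bilirubin is B and baseline bilirubin is B0, all in multiples of ULN. Row limits are from Table 11 and the definition is from Appendix E 2. Table 3 caps baseline ALT and AST at 2.5. Abnormal baseline is not defined, so it is assumed here to mean ALT or AST above ULN.

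**Logic, with B0 ≤ 1.**
1. Potential Hy's Law: A ≥ 3 and B ≥ 2.
2. B ≥ 2 then implies B > 1, B > B0 and B ≥ 2 × B0. Bilirubin is raised whether elevation means above ULN, ≥ 2 × ULN, above baseline or ≥ 2 × baseline. All three withhold rows are excluded.
3. The bilirubin part of the discontinue row is met, so that row turns on A ≥ 3 × A0 alone.
4. No row applies when 3 ≤ A < 3 × A0. The upper end cannot exceed 3 × 2.5 = 7.5, so the > 20 × ULN row never applies in this range.
5. The combined row reads and/or, so both ALT and AST must stay below 3 × their own baselines.

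**Size of the uncovered range.**

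| Baseline ALT (× ULN) | 3 × baseline | Uncovered on-study ALT (× ULN) |
|---|---|---|
| 1.2 | 3.6 | 3.0 to < 3.6 |
| 1.5 | 4.5 | 3.0 to < 4.5 |
| 2.0 | 6.0 | 3.0 to < 6.0 |
| 2.5 | 7.5 | 3.0 to < 7.5 |

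**Paired examples (ALT/bilirubin, × ULN).**
- Baseline ALT and AST 2.0, bilirubin 0.8. On study 4.0/0.8: withhold (> 3.5 to 5 row). On study 4.0/2.2: 4.0/2.0 = 2.0 × baseline ALT and 2.2/0.8 = 2.75 × baseline bilirubin, so no row.
- Baseline ALT and AST 2.5, bilirubin 0.8. On study 7.0/0.8: withhold (> 5 to 8 row). On study 7.0/3.0: 7.0/2.5 = 2.8 × and 3.0/0.8 = 3.75 ×, so no row.
- AST check: baseline ALT 2.0, AST 1.0, bilirubin 1.0. On study ALT 4.0, AST 2.5, bilirubin 2.2: no row. With AST 3.2 (3.2 × its baseline), the discontinue row applies.

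From 3.0 to 3.5 × ULN, normal bilirubin matches no row either, so the reversal occurs only above 3.5 × ULN.

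**Grid check.** The grid used baseline ALT 1.1 to 2.5, baseline bilirubin 0.3 to 1.0, on-study ALT 3 to 22 and bilirubin 2 to 6, with one transaminase modelled. Of 103,140 potential Hy's Law points, 12,960 had no row. All of them lay in the range in step 4, and no point in that range had a row. The result was the same with elevation read as > ULN, ≥ 2 × ULN or ≥ 2 × baseline. These counts show coverage of the rule, not how often patients would fall there.

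With baseline bilirubin above ULN, the outcome depends on how elevation is read, so those patients are outside the claim.

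**The case against.** The strongest reply is that these patients are not left unattended.

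- Section 10.6.6.3 lists potential Hy's Law under non-haematologic DLTs, and the general sentence in 6.6.6.3 covers a related DLT. Its pointer to 6.6.6.4 can be read as a cross-reference rather than an exclusion.
- Section 6.6.6.1 leaves dose modification to the Investigator's discretion, so even the withhold rows are less than absolute.
- Section 6.6.7 requires Study Physician contact for scenarios that are not described. Appendix E 4.2 requires an SAE report within one day and brings in the Study Physician. Section 8 requires prompt Sponsor discussion of immediate safety concerns.
- Baseline-relative limits look deliberate. The amendment summary shows that Table 11 was added for these patients, and Appendix E 6 also judges some cases against the patient's earlier state.

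Most of this stands and limits the point. It does not supply the missing instruction. The wording in 6.6.6.3 allows a reduction instead of a hold, and the Table 9 heading excludes hepatic changes. Section 6.6.6.1 also says that treatment should be modified or stopped for the events that the section describes, and Table 11 does not describe this one. Appendix E 4.2 and E 5 govern reporting and review and name no hold. The relatedness condition does not dispose of the point either, because E 4.2 has the case reported as related.

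A reader might infer that weekly infusions would continue through the 15 calendar days in E 5. The documents do not support that: 15 days is a limit for reporting to health authorities, and E 5 asks for Study Physician contact as soon as possible. A reader might also infer that Table 11 ought simply to repeat Table 10. That does not follow, because a baseline-relative discontinuation rule is a defensible choice for patients who enter with raised values.

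**Conclusion.** The gap is real and follows from the text. With baseline ALT or AST above ULN and baseline bilirubin at or below ULN, a concomitant rise to ALT or AST ≥ 3 × ULN and bilirubin ≥ 2 × ULN matches no row of Table 11 while both transaminases are below 3 × own baseline. Above 3.5 × ULN, the bilirubin rise removes an instruction that would otherwise apply. The range reaches just under 7.5 × ULN at the entry limit. General safeguards soften the effect, but none states a hepatic hold for this case.

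The point goes no further than that. It would be wrong to infer that DLT counts, SAE reporting or the SAP liver tables are affected, because they use the ULN limits. Nor do the documents show that such patients would in practice continue to be dosed, or how many there would be. The conclusion rests on reading abnormal baseline as ALT or AST above ULN. This is a cheap improvement for patient safety.

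**What to change.** Keep the baseline-relative discontinue row and make three changes to Table 11.

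1. **Add a row:** ALT and/or AST ≥ 3 × ULN with concomitant bilirubin ≥ 2 × the greater of ULN and baseline, not meeting the discontinue row, any occurrence. Action: withhold AZD0466 pending the Appendix E 5 review; discontinue if no alternative explanation is agreed; otherwise any restart follows section 6.6.7.
2. **Define the absence of bilirubin elevation** in the other rows as bilirubin below that same limit.
3. **State the order of precedence:** discontinue rows, then the new row, then the restart rows.

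Requiring a concomitant rise matters, because Appendix E 2 sets no timeframe between the two elevations and a bare reference to it would be broader than Table 10. Using the greater of ULN and baseline makes the limit continuous: 2.0 × ULN for baseline bilirubin up to 1.0, 3.8 for 1.9 and 4.0 for 2.0. No separate rule for Gilbert's syndrome is needed.

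With baseline bilirubin at or below ULN, the gap closes. A narrow band remains when baseline bilirubin is above ULN. For example, at baseline 1.4 the limit is 2 × 1.4 = 2.8, so bilirubin 2.2 with ALT 3.2 × ULN still goes to 6.6.7; the same bilirubin with ALT 4.0 falls in a withhold row.

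The cost is one row, one definition and one precedence note. Clinical chemistry is already scheduled on every dosing day, so no tests are added. The downside is an unknown number of additional reversible holds, some for modest transaminase rises. For example, baseline ALT 2.5 and bilirubin 1.0 rising to 3.0 and 2.0 × ULN is 3.0/2.5 = 1.2 × baseline ALT, and dosing would be held pending review.
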